5.4.3.2.5 Analysis of Lipase, Amylase, and Eosinophils

Laboratory values (including corresponding normal ranges) will be used for shift tables/figures, patient profiles and aggregated plots.

Tables summarizing shifts from baseline to maximum post-baseline CTCAE for increase in lipase and amylase will be presented. The grades to be used for amylase and lipase are defined by CTCAE Version 5.0 as follows:

- Grade 0: \leq ULN
- Grade 1: $>$ ULN – 1.5 x ULN
- Grade 2: $>$ 1.5 – 2.0 x ULN
- Grade 3: $>$ 2.0 – 5.0 x ULN
- Grade 4: \geq 5.0 x ULN

Grade 0 is not defined per NCI-CTCAE but will be used in derivations for simplicity to indicate that evaluable measurements are available.

Tables summarizing shifts from baseline to maximum post-baseline result for increase in eosinophils will be described according to the categories low, normal, and high.

The summary of these laboratory parameters will also include a “Missing” and “Total” category.

The aggregated line plots will be presented for study participants with increase in lipase and amylase with Grade 1 and above (i.e., $>$ ULN) and with high results in eosinophils. The line plots will be presented by laboratory parameter (amylase, lipase, eosinophils).

5.4.3.3 Vital Signs

Vital signs (temperature, pulse rate, respiratory rate, and blood pressure) will be collected throughout the study.

5.4.3.3.1 Vital Sign Values Over Time

Observed values and changes from Baseline will be summarized by vital sign variables and by scheduled visit.

The number and percentage of participants who meet each of the marked abnormality criteria outlined in Appendix 6.2 will be summarized at each scheduled visit and at any visit (including unscheduled visit).

Repeated and unscheduled measurements will be handled as described in Section 5.1.1.8.

5.4.3.3.2 Individual Subject Changes of Vital Sign Values

The Vital Signs that are categorized as normal, high or low based on the reference will be presented in shift tables from Baseline to each scheduled post-Baseline visit and any post-Baseline visit (including unscheduled visit).

A by-participant listing of all vital sign measurements and change from Baseline will be presented. The listing will include a flag for values identified as markedly abnormal.

5.4.3.4 Electrocardiograms

The following variables will be reported:

- Heart rate (beats/min)
- PR interval (ms)
- RR interval (ms)
- QRS duration (ms)

- QT interval (ms)
- QT corrected for heart rate using Fridericia's formula ($QTcF = QT/RR^{1/3}$) (ms)

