If a study participant has  $>$ ULN ALT, AST, or ALP that does not meet the exclusion limit at Screening, repeat the tests, if possible, prior to dosing to ensure there is no further ongoing clinically relevant increase. In case of a clinically relevant increase, inclusion of the study participant must be discussed with the Medical Monitor.

Tests that result in ALT, AST, or ALP up to 25% above the exclusion limit may be repeated once for confirmation.

11. QTc interval  $>450$ msec for male participants, QTc  $>470$ msec for female participants, or QTc  $>480$  msec in participants with bundle branch block.

NOTE: The QTc is the QT interval corrected for heart rate according to Fridericia's formula (QTcF). It is either machine read or manually overread.

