### **8.2.3 Electrocardiogram**

A 12-lead ECG will be obtained as outlined in the Schedule of Activities (see [Section 1.3](#)) using an ECG machine that automatically measures the heart rate and measures PR, QRS, QT, and QTc intervals. Refer to [Section 7](#) for QTc withdrawal criteria and any additional QTc readings that may be necessary.

All ECG recordings should be taken with the study participant resting in the supine position for at least 5 minutes before the recording.

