5.4.3.2.4 Assessment of potential liver toxicity	Liver Function Tests criteria changed from “LFT > * x ULN” to “LFT \geq * x ULN”	Update is according to the UCB internal guidance for LFT standard shells issued on 18 January 2024.
5.4.3.4 Electrocardiograms	Units are added at the ECG assessments	To provide further clarity
5.4.3.6 Columbia-Suicide Severity Rating Scale (C-SSRS)	
 The following text is added: C-SSRS instrument recorded at screening visit references the lifetime period and the past six months period. Baseline to end of study visit summaries reference the period prior to the visit assessed. The following underlined text is added: “Results of the C-SSRS, as well as the treatment emergent item at Week 12 (or (early) withdrawal will be summarized in SS by scheduled timepoint using the number of participants and percentage with.” 
[REDACTED]
 
[REDACTED]
	
 C-SSRS has two versions: 
 Screening/Baseline version Since last visit version Text has been added for further clarity. C-SSRS is also recorded at the (early) withdrawal visit. Also the “complete suicide item” is not subject to the “C-SSRS Screening/Baseline version”
6.1 Baseline characteristics and demographics	Weight (kg) categories are changed from “<56, 56-<77, 77 - <150, \geq 150” to “<43, 43 - <56, 56-<77, 77 - <150, \geq 150”	To reflect the protocol defined categories.
6.1.4.3 MG Specific Prior and Concomitant Medications	
 “IVIG, SCID and Immunoglobulins NOS” terms are removed from Group D. Following treatments are added: Plasmapheresis is added in Group D: 	
 IVIG or SCIG were included in both Group B and Group C For completeness in MG treatment therapies.

	Galantamine is added in Group F Rozanolixizumab is added in Group H	
6.1.6 AEs on Interest	
Injection site reactions derivation is added at Table 6-5: AEs of Interest selection criteria:
 
TEAE with HLT='Injection site reactions' or HLT='Administration site reactions NEC'
	Injection site reactions derivation is missing from the previous SAP version.

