5.4.3.4.1 Electrocardiogram Values Over Time

Observed values and changes from Baseline will be summarized at scheduled visit and by ECG variable. Baseline value will be based on the screening visit as ECG is not performed on Day 1.

The number and percentage of participants who met each of the marked abnormality criteria outlined Section 6.2.3 will be summarized at each scheduled visit and at any visit (including unscheduled visit).

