5.4.3.4.2 Individual Participant Changes of Electrocardiograms Values

The number and percentage of participants with normal, abnormal not clinically significant and abnormal clinically significant, not evaluable and not done ECG results will be provided in a shift table from Baseline to worst post-Baseline interpretation during the study.

A listing of electrocardiogram data will be presented, including repeated and unscheduled measurements.

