6.2.3 Marked Abnormalities Electrocardiogram (ECG)

Abnormality criteria to be applied in the assessment of ECG parameter values are given below:

Table 6–10: Marked Abnormalities (ECG)

Parameter	Treatment Emergent Markedly Abnormal Criteria
QT interval (ms)	$\geq 500\text{ms}$ $\geq 60\text{ms}$ increase from Baseline
QTcF (ms)	$\geq 500\text{ms}$ $\geq 60\text{ms}$ increase from Baseline
PR interval (ms)	Treatment-emergent value $>200\text{ms}$
QRS interval (ms)	Treatment-emergent value $>100\text{ms}$
Heart Rate (bpm)	$<50\text{bpm}$ $>120\text{bpm}$

Abbreviations: bpm = beats per minute; ms = milliseconds; QTc(F) = Fridericia corrected QT interval;

Note: Treatment-emergent is defined as meeting the MA criteria at any post-Baseline visit after the first dose of IMP and not meeting the MA criteria at Baseline.

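### SAP 5.4.3.4 lists RR in ms but gives a QTcF formula that returns ms only with RR in seconds; if QTcF is derived as written, every value is ten times too small

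*SAP*

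**What the plan says.** SAP Section 5.4.3.4 lists the ECG variables to be reported. RR appears as "RR interval (ms"), QT is also in ms, and QTcF is given by the "formula ($QTcF = QT/RR^{1/3}$) (ms"). Nothing there says that RR is in seconds or is divided by 1000.

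QTcF then enters three outputs:

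- Section 5.4.3.4.1: "Observed values and changes from Baseline will be summarized at scheduled visit and by ECG variable". The same section counts participants who meet the marked-abnormality criteria, at each visit and at any visit.
- Section 5.4.3.4.2: "A listing of electrocardiogram data will be presented, including repeated and unscheduled measurements".
- Table 6-10 in Section 6.2.3: the criteria for QTcF are at least 500 ms, and an increase of at least 60 ms from Baseline. The footnote identifies the variable: "QTc(F) = Fridericia corrected QT interval".

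The SAP does not name the source of QTcF. Protocol Section 8.2.3 describes a machine that "automatically measures the heart rate and measures PR, QRS, QT, and QTc intervals". The note to exclusion criterion 11 in Protocol Section 5.2 defines QTc as the Fridericia value and adds: "It is either machine read or manually overread".

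**The concern.** The formula and the units beside it do not fit together. Fridericia's correction divides QT by the cube root of RR in seconds, so that at RR = 1 second (60 beats per minute) QTcF equals QT. With RR in ms, the divisor at that rate is 10 instead of 1.

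If a programmer derives QTcF from the SAP text with the listed units, all values fall to about a tenth of their true size. The two QTcF rows of Table 6-10 would then be empty whatever the data showed. These rows are part of the analysis of ECG, which is one of the trial's other safety endpoints.

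**Working it through.** The documents state no numerical QTcF result, so there is no figure of the plan's own to reproduce. The check evaluates the formula under both unit choices.

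**Inputs from the SAP.** Section 5.4.3.4: QTcF = QT/RR^(1/3), with QT, RR and QTcF all in ms. Table 6-10: limits of 500 ms and a 60 ms increase.

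**Inputs assumed for illustration, not in the documents.** QT of 400 or 470 ms; RR of 500 to 1200 ms (heart rate 120 down to 50 beats per minute).

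**Step 1, the ratio.** With RR in ms:

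- as written: QT / RR^(1/3)
- RR in seconds: QT / (RR/1000)^(1/3) = 1000^(1/3) × QT / RR^(1/3) = 10 × the value as written

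The factor is exactly 10 at every heart rate.

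**Step 2, examples.**

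| QT (ms) | RR (ms) | As written | RR in seconds |
|---|---|---|---|
| 400 | 1200 | 37.6 | 376.4 |
| 400 | 1000 | 40.0 | 400.0 |
| 400 | 800 | 43.1 | 430.9 |
| 400 | 600 | 47.4 | 474.3 |
| 400 | 500 | 50.4 | 504.0 |
| 470 | 800 | 50.6 | 506.3 |

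The last two rows meet the 500 ms criterion when RR is in seconds and miss it by a wide margin as written.

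**Step 3, QT needed to reach 500.** As written, this is 500 × RR^(1/3) with RR in ms. With RR in seconds, it is one tenth of that.

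| RR (ms) | QT needed as written (ms) | QT needed with RR in seconds (ms) |
|---|---|---|
| 500 | 3969 | 397 |
| 600 | 4217 | 422 |
| 800 | 4642 | 464 |
| 1000 | 5000 | 500 |
| 1200 | 5313 | 531 |

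**Step 4, the 60 ms increase.** A rise of 60 in the value as written corresponds to a true rise of 60 × 10 = 600 ms in QTcF.

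A QT of about 4 to 5 seconds, or a QTcF rise of 600 ms, is not realistic. Under literal derivation both QTcF rows of Table 6-10 would show no participants.

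**The case against.** The strongest reply is that the formula is a label and not a programming instruction.

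- Section 5.4.3.4 is a list of variables to report, and the bracketed formula may only identify which correction is meant.
- The Version History for Amendment 3.0 says "Units are added at the ECG assessments", for clarity. This suggests that the ms tags are display units.
- The protocol describes a machine-measured QTc, and a QTcF that is machine read or overread for eligibility. RR is not among the intervals that Protocol Section 8.2.3 names.
- SAP Section 1 places table, figure and listing specifications in a separate document, which may settle the source and the units.
- The named method, the ms output and the 500 ms limit all imply RR in seconds, so a competent programmer would convert.
- A QTcF near 40 beside a QT near 400 would stand out in the summaries and listings.

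Most of this stands and limits the consequence. A collected QTcF is the likelier source, and an error of this size would probably be caught. It does not make the printed formula right. The exclusion-criterion note governs eligibility and does not fix the source for analysis. The specifications are not available here, and they would not correct the SAP text in any case. The SAP also shows that it can handle units: its eGFR footnote in Section 6.2.1 gives separate constants for creatinine in mg/dL and in umol/L. QTcF has no such statement.

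**Conclusion.** The concern holds, as a minor and conditional point. The formula in SAP Section 5.4.3.4 is inconsistent with the units listed beside it, by exactly a factor of 10. If QTcF is derived as written, the QTcF rows of Table 6-10 are in effect disabled, and the QTcF summaries and listings are wrong by the same factor. If QTcF is taken from the ECG reading, or RR is converted in programming, the effect is zero. The documents do not settle which applies.

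The following are unaffected in either case: the uncorrected-QT rows of Table 6-10, the shift table of ECG interpretations, the adverse-event endpoints and the MG-ADL noninferiority test. Site review under Protocol Section 7.1.2 uses the ECG printed at collection and does not depend on the SAP formula.

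The factor of 10 rests on no assumption about the data. Only the worked examples use assumed QT and RR values.

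**What to change.** In SAP Section 5.4.3.4, either write QTcF = QT/(RR/1000)^(1/3) with QT and RR in ms, or state that QTcF is the machine-read or overread value and is not derived. Then check the ECG program against that statement. The cost is one line of SAP text and one program check, with no change to data collection.

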5.4.3.4.1 Electrocardiogram Values Over Time

Observed values and changes from Baseline will be summarized at scheduled visit and by ECG variable. Baseline value will be based on the screening visit as ECG is not performed on Day 1.

The number and percentage of participants who met each of the marked abnormality criteria outlined Section 6.2.3 will be summarized at each scheduled visit and at any visit (including unscheduled visit).

5.4.3.4.2 Individual Participant Changes of Electrocardiograms Values

The number and percentage of participants with normal, abnormal not clinically significant and abnormal clinically significant, not evaluable and not done ECG results will be provided in a shift table from Baseline to worst post-Baseline interpretation during the study.

A listing of electrocardiogram data will be presented, including repeated and unscheduled measurements.

5.4.3.5 Physical examination

Results of clinically significant physical examination abnormalities were reported as adverse events. No additional listing will be provided.

[figure not shown]
5.4.3.6 Columbia-Suicide Severity Rating Scale (C-SSRS)

C-SSRS instrument recorded at screening visit references the lifetime period and the past six months period. Baseline to end of study visit summaries reference the period prior to the visit assessed.

[figure not shown]
Results of the C-SSRS, as well as the treatment emergent item at Week 12 (or (early) withdrawal will be summarized in SS by scheduled timepoint using the number of participants and percentage with:

1. suicidal ideation,
2. suicidal behavior,
3. suicidal ideation or behavior,
4. self-injurious behavior without suicidal intent.

Suicidal ideation is defined as an event in any of the following 5 categories:

Suicidal behavior is defined as an event in any of the following 5 categories:

Suicidal behavior or ideation is defined as an event in any of the above 10 categories.

Self-injurious behavior without suicidal intent is corresponding to the response to [REDACTED] in questionnaire.

The treatment emergent item at Week 12 is defined as any item that is present at Week 12 that was not present at Baseline.

A by- participant listing of the C-SSRS questionnaire data will be provided.

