**Table 1-2: Schedule of Activities**

Study Period	Screening Period a	Main Treatment Period							Extension Treatment Period	EW/ Withdrawal Visit b,w	SFU Visit (In-clinic) c	Rescue Therapy Visit (If applicable) d
		Baseline e (In-clinic)	Week 1 (Phone call)	Week 2 (In-clinic)	Week 4 (Phone call)	Week 8 (Phone call)	Week 12 (In-clinic)					
Visit name	Screening Visit (In-clinic)											
Visit #	1	2	3	4	5	6	7	8, 9, 10...		–	–	–
Day	-14 or -56	1	8	15	29	57	84	168, 252, 336...		(Last dose +40 days)		
Visit Window f	±3d	±2d	±2d	±2d	±2d	±2d	±2d	±7d		±7d		
Procedure/activity												

a Up to and including the time of the Screening Visit, study participants will continue to receive their IV C5 inhibitor at the recommended dose regimen. The last regularly scheduled IV C5 inhibitor administration cannot occur beyond the Screening Visit (±3 days) to ensure approximately a 2-week (for eculizumab) or 8-week (for ravulizumab) interval between the last regularly scheduled IV C5 inhibitor administration and the first SC ZLP administration at the Baseline Visit, respectively.

b Following the first in-clinic administration of ZLP at Baseline and in-clinic education and training, all study participants will self-inject daily SC doses of study medication. During the Main Treatment Period, dosing on in-clinic study visit days should be withheld until all assessments have been completed. On days when rescue therapy is concurrently administered, dosing should be withheld until after administration of rescue therapy and PK/PD sampling.

w Participants who withdraw during the Extension Treatment Period will complete a Withdrawal Visit as soon as possible but no later than the next scheduled visit. At the Withdrawal Visit, only the following study assessments need to be completed: prior and concomitant medications, weight, pregnancy testing (for women of childbearing potential), C-SSRS, and collection of AEs.

x At the Week 12 Visit, ZLP dispensation only occurs for study participants continuing into the Extension Treatment Period.

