### **8.2.5        Suicidal risk monitoring**

Study participants being treated with ZLP should be monitored appropriately and observed closely for suicidal ideation and behavior or any other unusual changes in behavior.

Families and caregivers of study participants being treated with ZLP should be instructed to monitor participants for the emergence of unusual changes in behavior, as well as the emergence of suicidal ideation and behavior, and to report such symptoms immediately to the study Investigator.

Suicidality will be assessed by trained study personnel using the C-SSRS (Posner et al, 2011; Mundt et al, 2010). The "Screening/Baseline" version of the C-SSRS will be completed during the Screening Visit and the "Since Last Visit" version will be completed at all other time points detailed in the Schedule of Activities (Section 1.3). Criteria for participant withdrawal based on response to the C-SSRS and Investigator's judgment are defined in Section 7.2.

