5.1.1.1.3 Study periods

Based on the specific requirements of safety and efficacy analyses, one concept of the definition of periods need to be considered for the study, which will be defined in detail in the section below.

5.1.1.1.3.1 Study periods for safety and efficacy data

- Two study periods are included in this study, the Main Treatment Period and the Extension Treatment Period.

No efficacy data are collected during the Extension Treatment Period thus, for efficacy analyses, only the Main Treatment Period will be considered.

The safety analyses will be performed on the Main Treatment Period as well as on the Overall Treatment Period. The Overall Treatment Period is constituted of the Main Treatment Period and of the Extension Treatment Period. The following definitions for completing study periods will be applied:

- A participant is considered to have completed the Main Treatment Period if he/she completed the Week 12 visit and:
 - Decided to enter the Extension Treatment Period.
 - OR
 - Transitioned to commercially available ZLP directly after the Week 12 visit (no Withdrawal or SFU visit required).
 - OR
 - Decided not to enter the Extension Treatment Period and completed a SFU visit.
- A participant is considered to have completed the study if he/she completed the Main Treatment Period and:
 - Did not enter the Extension Treatment Period.
 - OR
 - Entered the Extension Treatment Period and:
 - withdrew from the Extension Treatment Period, discontinued ZLP, and completed the Withdrawal and SFU Visits.
 - transitioned to commercially available ZLP and completed the Withdrawal Visit. No SFU Visit is required.

The total duration of study participation in the Main Treatment Period for all participants will be up to approximately 20 or 26 weeks, including the following periods:

- Screening Period: 2 to 8 weeks
- Treatment Period: 12-weeks
- SFU Period: 40 days (after the last dose for patients who do not enter the extension period or do not transition to commercially available ZLP directly after the Week 12 visit).

The Extension Treatment Period is constituted of the following periods:

- Treatment period
- SFU period: 40 days, for participants that withdrew from the Extension Treatment Period

The end of the study is defined as the date of the last visit of the last participant in the study.

The following definitions for starting and entering the periods will be applied:

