5.1.1.1.4 Mapping of assessments performed at (Early) Withdrawal Visit

If a participant prematurely discontinues study drug at any time prior to Week 12 during the Main Treatment Period, the participant should return to clinic for a stand-alone EW Visit. If a participant withdrew during the Extension Treatment Period, the participant should perform a Withdrawal Visit. These assessments will be mapped to the next scheduled visit where each assessment is evaluated as per protocol. This approach means that there is a chance that EW (or Withdrawal) data will be mapped to different visits according to the schedule of assessments.

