5.4.3.2.3 Laboratory Marked abnormalities

Treatment-emergent marked abnormalities (TEMAs) in laboratory parameters will be summarized at each scheduled visit and at any visit (including unscheduled visit). Thresholds for defining marked abnormalities for relevant laboratory parameters are available in Appendix 6.2. Treatment-emergent is defined as meeting the MA criteria at any post-Baseline visit while the MA criteria are not present before dosing.

Listings will include a flag for values identified as TEMA.

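### The treatment-emergent C-SSRS item is tied to Week 12 (or withdrawal), so items first reported at a routine Extension visit or at SFU are shown but not counted as emergent

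*SAP*

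**What the plan says.** SAP 5.4.3.6 contains two sentences on emergence, and they differ. The definition takes the treatment-emergent item at Week 12 to be "any item that is present at Week 12 that was not present at Baseline". The sentence listing the outputs says that the C-SSRS results, "as well as the treatment emergent item at Week 12 (or (early) withdrawal will be summarized in SS by scheduled timepoint", are given as the number and percentage of participants with ideation, behavior, either of these, or self-injury without suicidal intent. The section also promises a by-participant listing. It gives no emergent rule for Extension visits or SFU.

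On analysis periods, SAP 5.1.1.1.3.1 states: "The safety analyses will be performed on the Main Treatment Period as well as on the Overall Treatment Period". SAP 5.7 adds that, at the final analysis, by-visit safety displays are given on the Overall Treatment Period only.

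In Protocol Table 1-2 the C-SSRS row is marked at Screening, Baseline, Week 12, the Extension visits, EW/Withdrawal and SFU. It is not marked at Weeks 1, 2, 4 or 8. Under Protocol 8.2.5 the Screening/Baseline form is used at Screening, and the Since Last Visit "version will be completed at all other time points detailed in the Schedule of Activities".

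**The concern.** An emergent count should answer a simple question: in how many participants did something appear on treatment that was not there before? Here the count looks at Week 12, or at withdrawal on the wider reading, while collection continues every 12 weeks in an open-ended Extension and once more at SFU.

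The form makes the gap matter. Each later assessment asks only about the time since the previous visit. Ideation reported at Week 24 need not be reported again at the Withdrawal Visit, so a later flagged visit cannot be relied on to pick it up. The emergent count for the Overall Treatment Period could therefore be lower than the data support, in a table that sits beside laboratory and ECG tables built on a wider rule.

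**Working it through.** No stated figure in the plan bears on this point, so the check compares definitions and then counts visits.

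**1. Emergent rules within the SAP**

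- C-SSRS (5.4.3.6): present at Week 12, absent at Baseline.
- Laboratory (5.4.3.2.3): "Treatment-emergent is defined as meeting the MA criteria at any post-Baseline visit while the MA criteria are not present before dosing".
- ECG (6.2.3, note to Table 6-10): any post-Baseline visit after the first dose, with the criterion not met at Baseline.
- Adverse events (5.4.2.1): onset from first dose to 40 days after the final dose, or to last contact if earlier.

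Of these four, only the C-SSRS rule is fixed to a single visit.

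**2. Whether withdrawal closes the gap**

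SAP 5.1.1.1.4 says of EW and Withdrawal Visits: "These assessments will be mapped to the next scheduled visit where each assessment is evaluated as per protocol". A C-SSRS at an Early Withdrawal Visit in the Main Treatment Period therefore maps to Week 12, the next visit at which it is scheduled, and is covered. A C-SSRS at an Extension Withdrawal Visit maps to the next Extension visit, where no emergent rule is defined. It is covered if the words about withdrawal in the summary sentence govern, and not covered if the definition and the mapping rule govern.

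**3. Visits covered**

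Let k be the number of routine Extension visits attended before the Withdrawal Visit. The documents do not fix k. Post-dose assessments are Week 12 (1), Extension (k), Withdrawal (1) and, where required, SFU (1).

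| Path | Post-dose C-SSRS assessments | Covered, wider reading | Covered, definition and mapping only |
|---|---|---|---|
| Completes Week 12, no Extension, SFU | 1+1 = 2 | 1 | 1 |
| Withdraws in Main Period, SFU | 1+1 = 2 | 1 | 1 |
| Extension, Withdrawal, SFU | 1+k+1+1 = k+3 | 2 | 1 |
| Extension, moves to commercial product (no SFU) | 1+k+1 = k+2 | 2 | 1 |

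For k = 1, 2, 3, 4 the third row gives 2 of 4, 2 of 5, 2 of 6 and 2 of 7 on the wider reading. The fourth row gives 2 of 3, 2 of 4, 2 of 5 and 2 of 6. In the third row the uncovered assessments number (k+3) − 2 = k+1: the k routine Extension visits and SFU.

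An any-post-Baseline rule covers every assessment in every row.

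**The case against.** The strongest reply is that nothing disappears. C-SSRS results are summarized by scheduled timepoint, SAP 5.1.1.1 takes its timepoints from the Schedule of Activities, and all responses are listed. Ideation at Week 24 would appear as a count and percentage at Week 24. Because the form covers only the time since the last visit, a reader can see that it arose on treatment. With 20 planned participants, a listing is easy to read. Protocol 9.4.1 promised only that listing, and Protocol Table 3-1 places the C-SSRS among the other safety endpoints. An event also reported as an AE within the 40-day window would count as a TEAE, and withdrawals are reported under disposition. All of this stands, and it limits the point to classification.

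A reader might infer that the Overall Treatment Period would report no emergent suicidality, or that one participant in 20 could be missed. The documents do not support either. Responses are displayed at every scheduled visit, the withdrawal wording arguably brings in one Extension assessment, and the TEAE route is separate. Nor is 20 necessarily the Extension denominator, since that period is optional.

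A reader might also cite footnote w of Table 1-2, which has "C-SSRS, and collection of AEs" in its list. That list concerns the Extension Withdrawal Visit only. Collection at routine Extension visits and SFU is shown by the C-SSRS row itself.

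Finally, the Baseline form looks back only over a Screening Period of about 2 or 8 weeks, so an item positive at Screening could later count as new. This is secondary. Exclusion criterion 7 removes lifetime attempts and past-6-month ideation at questions 4 or 5, leaving mainly lower-level ideation. The error is toward over-counting, and the choice of reference period is a matter of judgment.

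What the reply does not answer is why the C-SSRS emergent count should stop at Week 12 or withdrawal when the table, the period and the data do not. The TEAE route does not fill the gap either: the SAP derives no AE from a C-SSRS answer, and an SFU at 40 ± 7 days can fall as late as day 47.

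**Conclusion.** The point holds as a gap in the emergent definition. Items first reported at a routine Extension visit or at SFU are summarized and listed but not counted as treatment-emergent in the C-SSRS analysis. It is also unclear whether an Extension Withdrawal Visit is covered.

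On the wider reading, at most 2 of k+3 post-dose assessments are covered for a participant with Extension visits, a Withdrawal Visit and SFU, and 1 of 2 for a participant who stops at Week 12. These are counts of visits, not of expected cases. They assume visits take place as scheduled and that k, which the plan leaves open, is at least 1 for Extension participants. During Main Period treatment the rule is adequate, because Week 12 and Early Withdrawal are the only scheduled post-dose C-SSRS assessments before SFU.

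The primary endpoints and the MG-ADL test are unaffected, and no protocol commitment is broken. This is a worthwhile clarification of low severity.

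**What to change.** Replace the definition in SAP 5.4.3.6 with wording to this effect: a treatment-emergent C-SSRS item is one present at any post-Baseline assessment (Week 12, Extension, EW/Withdrawal, SFU or unscheduled) and not present at Baseline. Report the number and percentage of Safety Set participants with at least one such item for the Main and the Overall Treatment Periods, showing the denominator with observed data as SAP 5.1 already requires. Keep the by-timepoint summary and the listing.

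Two optional additions would help. Mark in the listing any emergent item that was also positive in the Screening past-6-month recall, and show the day relative to last dose for items reported at SFU.

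The cost is one SAP sentence and one derived flag. No new data are needed. If the tables have already been produced, the flag can be added from the existing C-SSRS dataset and described as a clarification.
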